## Physical Therapy and Deep Brain Stimulation in Parkinson Disease (PTDBS)

### III. Methods

#### Participants

Participants will be recruited from the community.

**Inclusion Criteria:** Participants with PD will be  $\geq 30$  years of age and have a neurological diagnosis of PD. PD diagnostic criteria include those used for clinically defined “definite PD”, as previously described by Racette et al. based upon established criteria. Each must have had clear benefit from levodopa and meet the other inclusionary and exclusionary criteria below.

All participants will meet the following inclusion criteria:

- 1) At least one year post-surgery for STN-DBS for PD
- 2) No evidence of dementia (MMSE  $\geq 24$ ).

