## Physical Therapy and Deep Brain Stimulation in Parkinson Disease (PTDBS)

### **Baseline Testing**

Baseline testing will be conducted with participants in two conditions: 1) OFF stimulation / OFF medication, 2) ON stimulation / ON medication. These conditions will be tested on two separate days within one week of each other and the order of conditions will be randomized. The OFF stimulation / OFF medication and ON stimulation / ON medication testing sessions will occur on two separate days to avoid fatigue. Regardless of testing condition, upon arriving for the first laboratory visit, informed consent will be obtained from each participant.

**Informed Consent and MMSE:** Participants will be consented in a private room with only the participant and study team members present. Participants will first receive a verbal explanation of the study and then be given as much time as they wish to read the consent form and ask any questions they may have. Participants will provide written informed consent prior to commencing study participation.

The Mini-Mental Status Examination (MMSE) will be conducted first only in the ON stimulation / ON medication condition. If the participant scores less than 24/30, the participant will be excluded from further participation at this time. If the score is 24 or above, the baseline assessment will proceed. After completing the MMSE in the ON stimulation / ON medication condition, each participant will complete the battery of balance, walking, and motor function tests.

For the OFF stimulation / OFF medication condition, participants will arrive to the laboratory in the practically defined off-state of their medication cycle (i.e.  $\geq 12$  hours since last dose). The deep brain stimulators will be turned off and the participant will then wait 45 minutes until the physical assessment begins. After 45 minutes, each participant will complete a battery of balance, walking, and motor function tests.

Upon completion of the baseline visits, the participant will be randomized to either the intervention or control group.

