### **Safety and Adverse Events**

The research team will do everything possible to ensure safety of all participants over the course of this study. Potential adverse events related to this study may include falls with serious injury, major cardiovascular incidents, or serious injuries associated with physical activity. The Adverse Event tracking form will be completed weekly with every participant. The adverse event most likely to occur in this study is a participant fall due to walking. Members of the research team will all be trained in fall prevention and will closely monitor all participants throughout all aspects of the study in case of a need to assist with balance to prevent a fall. In the case of a serious adverse event, emergency medical care will be sought immediately if needed. Any serious adverse events will be reported to the local IRB in accordance with their policies and procedures.

These risks will be addressed in the following ways:

- a) Effects of withholding overnight and morning anti-PD medications: Participants may experience a temporary worsening of your Parkinson's disease symptoms as a result of not taking their anti-Parkinson's medication for study evaluations. Once taking the medication, the symptoms should return to their typical levels. Effects of medication withdrawal will be monitored and if the effects are too severe, participants will immediately take their medication. At that point, the study will be discontinued.
- b) Effects of turning off deep brain stimulators: Participants may experience a temporary worsening of your Parkinson's disease symptoms as a result of turning off the deep brain stimulators for study evaluations. Once we turn the stimulators on, the symptoms should return to their typical levels. Effects of stimulation withdrawal will be monitored and if the effects are too severe, participants will immediately have their stimulators turned on. At that point, the study will be discontinued.

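### The MMSE is given only at the ON/ON baseline visit while visit order is randomised, so some ineligible candidates can undergo OFF/OFF testing before they are excluded

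*Combined protocol and SAP*

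**What the plan says.** The Participants section makes an MMSE score of at least 24 an inclusion criterion. Baseline Testing then sets out two assessments, OFF stimulation / OFF medication and ON stimulation / ON medication. On their timing it says "These conditions will be tested on two separate days within one week of each other", and on their sequence "the order of conditions will be randomized".

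The cognitive check belongs to one of the two visits: "The Mini-Mental Status Examination (MMSE) will be conducted first only in the ON stimulation / ON medication condition". The consequence of a low score is applied there: "If the participant scores less than 24/30, the participant will be excluded from further participation at this time".

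The OFF/OFF paragraph contains no cognitive check. In that condition "participants will arrive to the laboratory in the practically defined off-state of their medication cycle", defined as 12 hours or more after the last dose. Then: "The deep brain stimulators will be turned off and the participant will then wait 45 minutes until the physical assessment begins". The balance, walking and motor tests follow.

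The only earlier eligibility step is the phone screen in the Protocol section. Its content is not described and no cognitive test is named.

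**The concern.** An entry criterion should be settled before a candidate undergoes a study procedure that carries risk. Here, for anyone drawn OFF/OFF first, the order is reversed. The protocol itself names risks of that visit under Safety and Adverse Events. Item a covers medication withdrawal, and item b says: "Participants may experience a temporary worsening of your Parkinson's disease symptoms as a result of turning off the deep brain stimulators for study evaluations". Items d and e recognise stumbling and falling during assessments. The BESTest tasks described under Measures include standing on one leg and standing on foam with eyes closed.

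A person then excluded on the MMSE is never randomised and contributes to none of the Specific Aims. The burden and risk were avoidable and bought no information. The text is also at odds with itself: it makes a passing score the condition for the baseline assessment to go ahead, yet an OFF-first candidate may already have completed one of the two baseline assessments by then.

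This is separate from the timing of consent. Taking consent earlier would still leave the MMSE after an OFF-first visit.

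**Working it through.** The documents state no figure on this point, so there is none to reproduce. The check has two parts.

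**1. Sequence, from Baseline Testing**

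| Order drawn | First visit | Second visit | When MMSE below 24 is found |
|---|---|---|---|
| ON/ON first | Consent, MMSE, tests | OFF/OFF tests | Before any OFF/OFF testing |
| OFF/OFF first | Consent, stimulators off, 45-minute wait, tests (medication already withheld on arrival) | MMSE, then ON/ON tests | After the OFF/OFF visit, up to a week later |

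The phrase placing the MMSE first and only in the ON/ON condition is loose, but no reading of it puts an MMSE ahead of an OFF/OFF visit that comes first.

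**2. Size**

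Inputs:
- Places to fill: 2 × 17 = 34 (Power section).
- p, the probability that OFF/OFF comes first: 1/2, **assumed**. The 1:1 ratio under Randomization Method concerns treatment group, not visit order.
- q, the share of candidates reaching the laboratory with MMSE below 24: not given, so **assumed** at 2% to 20%.

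The expected share of MMSE failures tested OFF/OFF first is p = 50%. If the unstated ratio were 1:2 or 2:1, it would be 33% or 67%.

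Expected numbers: candidates tested = 34/(1 − q); failures = q × 34/(1 − q); exposed = p × failures.

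| q | Tested | Failures | Exposed (p = 1/2) |
|---|---|---|---|
| 2% | 34/0.98 = 34.7 | 0.69 | 0.35 |
| 5% | 34/0.95 = 35.8 | 1.79 | 0.89 |
| 10% | 34/0.90 = 37.8 | 3.78 | 1.89 |
| 20% | 34/0.80 = 42.5 | 8.50 | 4.25 |

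The chance that at least one of k failures is tested OFF/OFF first is 1 − (1 − p)^k. With p = 1/2 this is 50%, 75%, 87.5% and 93.8% for k = 1, 2, 3 and 4.

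**The case against.** The strongest reply is that the effect may be close to nil. The phone screen is meant to establish eligibility and may already remove people with evident cognitive impairment. No failure rate is given, and at 2% the expected number exposed is well below one. This stands as a limit on size. It does not remove the gap, because the phone screen names no cognitive test and the laboratory exclusion rule presupposes that some candidates will fail there.

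A second reply is that safeguards exist. Withdrawal effects are described as temporary and are monitored, the session ends if they are too severe, and breaks or termination are provided for if someone appears unsteady. This also stands: not everyone tested OFF/OFF first would complete the visit. The safeguards limit harm but do not make the exposure necessary.

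A third reply is that randomised order is a deliberate feature. With ON/ON always first, every baseline OFF/OFF score would come from a second encounter with the tests, and the plan never says which condition is primary for efficacy. That is a real cost. However, the order would be the same in both arms, no Specific Aim compares ON with OFF, and the model in the Statistical Analysis Plan has only group, time and their interaction.

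A reader might infer more than the text supports:
- **That the trial's results are compromised.** They are not: group assignment is revealed only after both baseline visits.
- **That OFF/OFF testing is the most dangerous part of the study.** The documents do not rank it so. They name a fall due to walking as the most likely adverse event, and walking occurs at both visits and in the intervention.
- **That each exposed person undergoes a baseline visit of about 3 hours.** That duration is stated under Follow-Up Testing. Carrying it back to baseline is a reasonable inference, not a stated figure.

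**Conclusion.** The point holds as a matter of sequence: as written, a candidate drawn OFF/OFF first is tested in that state before the MMSE criterion is checked. About half of the MMSE failures who reach the laboratory would be affected if order is 1:1. In absolute terms that is roughly 0.3 to 4.3 people over assumed failure rates of 2% to 20%. The sequence is certain from the text. The counts are only as good as the two assumptions, and the true number may be zero or one.

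What is at stake is avoidable burden and risk for a few people who cannot enter the trial. The PT-versus-control comparison, power and type I error are untouched. The change is worth making because it protects participants at little cost, not because any conclusion depends on it.

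**What to change.** Amend Baseline Testing so that the MMSE is completed in the ON/ON state before any OFF/OFF baseline testing. The simplest way is to make ON/ON the first baseline visit for everyone, so that the MMSE follows consent at that visit. This is a short edit with no added visit or staff. Its cost is that baseline ON-versus-OFF differences become confounded with visit order or practice.

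If the sponsor wants to keep randomised order, the alternative is an ON-state MMSE before the OFF/OFF visit for those drawn OFF/OFF first. That may need an extra contact, so the absence of added visits applies only to the fixed order.

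Eligibility gives no reason to change the order at 8 and 12 weeks. Because Follow-Up Testing says the baseline procedure is repeated, the amendment should state whether the new order carries forward. If it does, it is the same in both arms.

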### **Intervention**

Within one week of the initial visit, for the participants assigned to the PT group, the PT intervention will begin. Participants in the PT group will receive 8 weeks of the intervention, meeting 2 times per week for one hour each session.

**Physical Therapy:** This intervention will mirror traditional physical therapy for individuals with PD and will include exercises designed to improve balance, gait, and lower extremity strength. Balance exercises will follow a framework outlined by Schoneburg and colleagues targeting quiet stance, anticipatory and reactive postural adjustments, and dynamic postural control. Quiet stance exercises might include, but are not limited to, standing on a firm surface with eyes closed, standing on a foam surface with eyes closed, and standing in tandem (one foot in front of the other). Anticipatory postural adjustment exercises might include, but are not limited to, standing on one leg, sit-to-stand, and trunk rotation in standing with feet planted. Reactive postural adjustment exercises might include, but are not limited to, standing with perturbations from the physical therapist while on firm and foam surfaces and leaning forward, backward, or laterally and taking a step to regain balance when needed. Dynamic postural control exercises might include, but are not limited to, walking with head turns side-to-side, walking while bouncing a ball, and walking around

## Physical Therapy and Deep Brain Stimulation in Parkinson Disease (PTDBS)

an obstacle course. During every balance exercise, a physical therapist will be guarding the participant, who will be wearing a gait belt for safety. The gait belt will reduce the risk of falling by enabling the physical therapist to maintain contact with the participant at all times. Balance exercises following a similar framework improved balance and reduced falls in people with PD without STN-DBS. Balance exercises will be chosen using a decision tree to ensure exercises are sufficiently challenging to maximize the potential effect. For example, if a person is able to stand with feet together on a firm surface without significant sway on observation, the participant will then be asked to close their eyes to increase the challenge. Gait training exercises will include treadmill walking and practice with cueing strategies (e.g., auditory, visual) to improve gait and reduce freezing of gait. Treadmill walking will start at the participant's comfortable pace (measured during overground walking) and progress weekly provided the participant is able to tolerate it. Tolerance of treadmill walking will be determined by the observation of gait quality during treadmill walking and the participant's rating of perceived exertion (RPE) using Borg's Scale. If a participant's RPE rating exceeds 15 (i.e. Hard (heavy)) or the physical therapist determines that the gait quality is poor, the treadmill walking will be stopped. The treadmill is equipped with a wrist-band that, if detached from the treadmill, will stop the treadmill. Furthermore, there are two buttons on the treadmill that will allow the participant or physical therapist to stop the treadmill at any time. Each participant will be oriented to these safety features prior to starting treadmill walking. Both treadmill walking and cueing have been used to reduce gait variability and improve spatiotemporal gait parameters in people with PD without STN-DBS. To gain more information about how participants perceive the fatigue and challenges associated with each exercise, we will use a numeric rating scale (NRS). Participants will be asked on a scale of 0-10 how fatiguing and challenging they feel each exercise was after completing it. The attachment (NRS) will be shown to the participant each time the question is asked. Each participant's ratings will be recorded on the physical therapy intervention protocol document. Finally, participants in the physical therapy group will be provided a home exercise program (HEP). The HEP will be designed to maintain or improve lower extremity strength. Lower extremity strengthening exercises will include repeated sit-to-stand, heel raises in standing, hip abduction, and standing half squats. Participants will receive a detailed handout that includes instructions on how to correctly and safely complete each exercise. Participants will perform the HEP twice weekly on days in which they are not attending a physical therapy session. Additionally, participants in the PT group will be asked to complete the HEP twice weekly during the 4 weeks between the post-test and follow-up assessments. Participants will track performance and completion of the HEP using the HEP Checklist. During the intervention, the forms will be returned to the study team at each physical therapy session. During the 4-week follow up period, each participant in the PT group will return the forms at the follow-up assessment visit. In addition to physical therapy, participants will be allowed to adjust anti-PD medication and STN-DBS settings as determined by their neurologist. To measure safety, participants assigned to the PT group will complete an Adverse Events tracking form with the physical therapist weekly during the intervention.

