#### Measures

**Adverse Events:** Adverse events will be measured using a questionnaire administered on a weekly basis.

**Feasibility of PT:** Feasibility of PT sessions will be measured by the number of sessions attended relative to the total possible number of sessions (i.e., 16).

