
### **Control Group**

The control group will not receive a prescribed physical therapy intervention and will be instructed to go about their daily lives as usual. They will be asked to avoid making changes to their daily routine or usual exercise program. Participants will be allowed to adjust anti-PD

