## Physical Therapy and Deep Brain Stimulation in Parkinson Disease (PTDBS)

medication and STN-DBS settings as determined by their neurologist. To measure safety, those assigned the control group will be called weekly and will complete the Adverse Events tracking form over the phone with a member of the study team.

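### Adverse events are asked about by the therapist in the PT arm and by phone in controls, without one stated window, and compared only as group totals: a low-severity gap in the Aim 1 comparison

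*Combined protocol and SAP*

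**What the plan says.** All references are to the combined protocol and SAP. Section I (Specific Aims) takes the count of adverse events as the primary safety variable. Hypothesis 1 is a between-arm statement: the PT arm should report no more events than controls.

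The instrument and its frequency are common to both arms. Under Measures, "Adverse events will be measured using a questionnaire administered on a weekly basis"; under Safety and Adverse Events, "The Adverse Event tracking form will be completed weekly with every participant".

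The way the form is completed differs:

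- Physical Therapy, under Intervention: "To measure safety, participants assigned to the PT group will complete an Adverse Events tracking form with the physical therapist weekly during the intervention".
- In the section on the Control Group: "those assigned the control group will be called weekly and will complete the Adverse Events tracking form over the phone". The other party to the call is a study team member, and no last call is specified.

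After week 8, "participants in the PT group will be asked to complete the HEP twice weekly during the 4 weeks between the post-test and follow-up assessments". The only paperwork described for that period is the home-exercise checklist: "During the 4-week follow up period, each participant in the PT group will return the forms at the follow-up assessment visit".

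The Statistical Analysis Plan gives total events by group for a qualitative comparison. The Power section says the study is not powered for a difference in adverse events.

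**The concern.** The group totals are the whole planned answer to Hypothesis 1, and Section II makes safety and feasibility the condition for later studies. Three features make those totals hard to read.

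- **Who asks, and how.** PT participants answer in person to the therapist who treats them; controls answer by phone. Participants know their allocation (Randomization Method). Familiarity with the therapist could bring out more reports, or reluctance to complain to that person could suppress them.
- **The window.** The PT form is tied to the intervention period. The control calls have no stated end, and the statement under Safety and Adverse Events has no time limit. Study-prescribed home exercise continues for four weeks after the intervention.
- **The summary.** Safety and Adverse Events names a fall as the likeliest event, and falls can recur in one person. A total does not separate many people affected from one person affected often. The trigger under Interim Monitoring and Early Stopping does consider whether falls involve more than one individual; the analysis plan does not.

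**Working it through.** The plan gives no adverse event rate, margin or power, so there is no stated figure to reproduce.

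**Inputs from the plan.** 17 recruited and 14 required per arm (Power); 8 weeks at 2 sessions per week (Intervention); weekly form in both arms (Measures, Intervention, Control Group); home exercise twice weekly for 8 weeks and then for 4 more (Intervention).

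**Step 1, enquiries.** Over 8 weeks, 1 × 8 = 8 scheduled forms per PT participant and 1 × 8 = 8 per control, reading the control calls as covering the same 8 weeks. The 2 × 8 = 16 PT sessions are treatment contacts, not adverse event enquiries.

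**Step 2, base case.** Person-weeks are 17 × 8 = 136 per arm. With equal true rates, windows and capture, the expected PT:control ratio of totals is 136/136 = 1.00. If 3 of 17 leave each arm at week 4 (timing assumed), each arm has 14 × 8 + 3 × 4 = 124 person-weeks and the ratio is still 1.00.

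**Step 3, mode of collection (illustration).** Ratio = PT capture / control capture. The 70–90% relative capture is assumed; the documents give no source.

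- Phone lower: 1/0.9 = 1.11 to 1/0.7 = 1.43.
- Therapist form lower: 0.90 to 0.70.
- With 10 true events per arm (assumed) the gap is 10 × 0.1 = 1 to 10 × 0.3 = 3. With 30 it is 3 to 9.
- If counts are Poisson (assumed), the chance SD of the difference is √(10 + 10) = 4.5 or √(30 + 30) = 7.7.

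The gap is thus below or near chance variation. As a further illustration, take 17 per arm and equal true rates of 0.05 to 0.25 events per participant-week (assumed), which is 136 × 0.05 = 6.8 to 136 × 0.25 = 34 true events per arm. The chance that the PT total exceeds the control total is then:

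| Capture, PT / control | P(PT total > control total) |
|---|---|
| 0.9 / 0.9 | 0.44–0.47 |
| 0.9 / 0.7 | 0.60–0.80 |
| 0.7 / 0.9 | 0.16–0.29 |

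**Step 4, window.** On the wording under Intervention, PT forms stop at week 8. Home sessions per PT participant are 2 × 8 = 16 and then 2 × 4 = 8, so 8/24 = 33% would follow the last weekly form. If control calls ran to week 12 while PT forms stopped at week 8, which the plan does not say, person-weeks would be 136 v 17 × 12 = 204 and the ratio 136/204 = 0.67 at equal rates.

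**Step 5, totals without a denominator.** One participant reporting a fall on each of 8 forms adds 8 events but is 1/17 = 6% of the arm. If the 3 early dropouts of Step 2 all fell in one arm, the ratio at equal rates would be 124/136 = 0.91 (PT arm) or 136/124 = 1.10 (control arm).

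**The case against.** Most of the comparison is already standardised: the same form, the same frequency and live administration in both arms. The caller could be a physical therapist, since the plan requires only a study team member. The comparison is openly descriptive and unpowered, the capture figures are assumed, and even then the gap is no larger than ordinary noise. An equal 8-week window is the natural reading, because Aim 1 concerns an 8-week intervention. Serious adverse events go to the IRB with no week-8 limit stated. Nothing in the analysis plan forbids reporting the number of participants affected.

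All of this stands as a limit on severity, and it rules out several stronger inferences that a reader might draw:

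- **PT participants are asked about events twice as often.** The 16 v 8 contrast sets treatment sessions against calls; scheduled enquiries are 8 v 8.
- **Falls seen in sessions bias the PT count upward.** They arise from exposure to PT, which is what Aim 1 sets out to count.
- **The windows are unequal.** No passage says so; they are only not stated to be equal.
- **The bias has a known direction or size.** The documents support neither.

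The objection does not remove the difference in who asks and by what means, the missing end date for control calls, or an analysis plan that commits only to totals.

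**Conclusion.** The point holds in a limited form, at low severity. Followed as written, the plan leaves collection mode, and possibly the window, tied to arm, and lets repeat events in one person dominate a total. No hypothesis test is affected because none is planned for adverse events. The stopping trigger is unaffected because it uses falls within PT sessions only.

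The expected distortion is nil (ratio 1.00) if capture and window are equal. Every other ratio above depends on an assumption about capture, dropout or call duration that the documents do not settle. What is at stake is whether a reader can interpret the Aim 1 result, not whether it is valid as a description of what was recorded.

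**What to change.** 1. **One window.** Reconcile Measures, Intervention, Control Group, and Safety and Adverse Events into a single collection period applied identically to both arms: at minimum weeks 1–8. If events in weeks 9–12 are collected, collect them in both arms and report them separately, since home exercise continues then. Stating the window costs a few lines. Extending the calls would add up to 17 × 4 = 68 per arm.

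2. **A fuller descriptive summary.** In the Statistical Analysis Plan, report for each arm the number of events, participants with at least one event, completed weekly forms (person-weeks), and events per person-week. Identify in-session events separately but keep them in the total. No test is needed, and the cost is a few lines.

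3. **Common collection, preferably.** Have a study team member other than the treating therapist administer the same weekly phone form in both arms. This means about 17 × 8 = 136 short calls to PT participants, by a team already phoning controls. The downside is some matching of duplicate reports between calls and session records, so that each event is counted once. If this is not affordable, state the mode difference as a limitation. In either case, state participants' knowledge of their allocation as a limitation, because a neutral caller does not remove it.

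Items 1 and 2 alone deal with the window and the denominator, but leave the mode difference in place.
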